4.3.1 Dose Modifications, Interruptions, and Discontinuation

Subjects will be monitored for adverse events (AEs) from the time of first study intervention (i.e., biopsy, if needed, or treatment, whichever comes first) through their last follow-up visit (i.e., 30 days after the date of the last dose of study treatment). Subjects will be instructed to notify their physician immediately at the onset of any AE. Causality assessment of AEs will be determined by the investigator. AE severity will be graded by the investigator in accordance with CTCAE v.4.03.

The following should be taken into consideration in decisions regarding dose modifications (reductions or interruption):

CONFIDENTIAL

- As a general approach all AEs should be managed with supportive care at the earliest signs of toxicity considered related to the study treatment. Should this be ineffective, dose interruptions and/or reductions should be considered to prevent worsening of toxicity.
- Dose modification criteria are shown in Table 4-3.
- Dose interruptions and/or reductions should be implemented for unacceptable toxicity. Doses may be modified at any time while a subject is on treatment.
- The assigned starting dose for cabozantinib is 40 mg/day, and the assigned starting dose for erlotinib is 100 mg/day. One dose reduction level of cabozantinib and one dose reduction level of erlotinib are permitted (see Table 4-2).
- Dose reductions or interruptions may also occur in the setting of lower grade toxicity than defined in Table 4-3 if the investigator feels it is in the interest of a subject's safety and will optimize drug tolerability.
- Interruption of treatment for treatment-related AEs may occur at any time per investigator discretion. If treatment is interrupted due to related AEs for more than 6 weeks, treatment should be discontinued unless there is unequivocal evidence that the subject is benefitting. In this situation, a subject may be able to restart therapy with a dose reduction upon resolution of the toxicity per the discretion of the investigator.
- Dose interruptions for reason(s) other than related AEs (e.g., surgical procedures) can be longer than 6 weeks per the discretion of the investigator.
- Subjects may continue on only one study drug if the other drug must be stopped altogether and physician believes there is clinical benefit to staying that drug.

Guidelines for the management of specific AEs are provided in Section 4.4.1.

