Table 4-2: Dose Reductions of Cabozantinib and Erlotinib

| Assigned Starting Dose | First Dose Level Reduction |
|-------------------------------|---|
| 40-mg cabozantinib oral qd | 20-mg cabozantinib oral qd (discontinue if this dose is not tolerated) |
| 100-mg erlotinib oral qd | 50-mg erlotinib oral qd (discontinue if this dose is not tolerated) |

See Section 4.5.5 for complete details regarding potential drug interactions.

CONFIDENTIAL

Table 4-3: Dose Modifications for Treatment-Related AEs for Cabozantinib and Erlotinib

Dose modifications should be made to both cabozantinib and erlotinib for any overlapping treatment-related adverse events unless the investigator suspects one drug over another to be the cause of unacceptable toxicity. In this case, dose modifications may be made to one drug per the investigator's discretion. The most common overlapping toxicities are: diarrhea, fatigue, nausea, skin reactions and vomiting.

| CTCAE v.4.03 Grade | Recommended Guidelines for Management^a |
|--|---|
| Grade 1 AEs | Add supportive care as indicated. Continue treatment at the current dose level if AE is manageable and tolerable. |
| Grade 2 AEs which are tolerable and are easily managed | Continue treatment at the current dose level with supportive care. |
| Grade 2 AEs which are intolerable and cannot be adequately managed | At the discretion of the investigator, treatment should be dose reduced or interrupted. Note: It is recommended that dose holds be as brief as possible. |
| Grade 3 AEs (except clinically non-relevant laboratory abnormalities) | Treatment should be interrupted unless the toxicity can be easily managed with a dose reduction and optimal medical care. Note: It is recommended that dose holds be as brief as possible. |
| Grade 4 AEs (except clinically non-relevant laboratory abnormalities) | Subjects should have treatment interrupted immediately. Discontinue treatment unless the following criteria are met: 
 • Subject is deriving clear clinical benefit as determined by the investigator and agreed by the sponsor-investigator • Toxicity can be managed with a dose reduction following recovery to Grade 1 (or baseline) and optimal medical care |

Note: The dose delay and modification criteria for specific medical conditions are provided in Section 4.3.1. For re-treatment criteria of study treatment after a dose hold see Section 4.3.2.

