4.3.2 Dose Reinstitution and Reescalation

If the subject recovers from his or her toxicities to CTCAE v.4.03 Grade ≤ 1 or to the baseline value (or lower) and the toxicity was unrelated to study treatment, then study treatment may be restarted with no change in dose.

CONFIDENTIAL

If the subject recovers from his or her toxicities to Grade \leq 1 or to the baseline value (or lower) the toxicity was deemed possibly related to study treatment, then study treatment may be restarted at a reduced dose (see Table 4-2 for the schedule of dose reductions).

Subjects receiving the lowest trial dose (cabozantinib = 20 mg/day; erlotinib = 50 mg/day) may be restarted at the same dose if deemed safe at the discretion of the investigator. Subjects unable to tolerate the lowest trial dose should discontinue study treatment.

Re-escalation to the previous dose, (but not higher than the trial dose [cabozantinib = 40 mg/day; erlotinib = 100 mg/day]) may be allowed at the discretion of the investigator and agreement of the PI for AEs which have resolved or recovered to Grade 1 (or baseline value) and deemed tolerable and easily managed by optimized supportive treatment. Dose re-escalation is not allowed for a drug-related dose reduction triggered by Grade 4 hematologic toxicities or by Grade 4 AEs affecting major organs (e.g., central nervous system, cardiac, hepatic, renal).

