| Grade 2 | Study treatment may be continued if PPES is tolerated. Study treatment should be dose reduced or interrupted if PPES is intolerable. Continue urea 20% cream twice daily AND clobetasol 0.05% cream once daily and add analgesics (e.g., non-steroidal anti-inflammatory drug (NSAID)s/gamma-aminobutyric acid agonists) for pain control if needed. Reassess at least weekly; if PPES worsens or affects self-care, proceed to the intervention guidelines for Grade 3. |
| Grade 3 | Interrupt study treatment until severity decreases to Grade 1 or 0. Continue treatment of skin reaction with clobetasol 0.05% cream twice daily AND analgesics. Resume study drug at a reduced dose if PPES recovers to Grade ≤ 1 . Discontinue subject from study treatment if PPES does not improve within 6 weeks. |

^a Permitted dose levels are defined by individual protocols.

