4.4.1.10 Corrected QTc Prolongation

The effect of orally administered cabozantinib 140 mg qd on QTc interval was evaluated in a placebo-controlled study in subjects with MTC. A mean increase in QTcF of 10-15 ms was observed after 4 weeks after initiating cabozantinib treatment. A concentration-QTc relationship could not be definitively established. Changes in cardiac wave form morphology or new rhythms were not observed. No cabozantinib-treated subjects in this study had a QTcF > 500 ms.

CONFIDENTIAL

Cabozantinib should be used with caution in subjects with QT prolongation risk, a history of QT interval prolongation, or who are taking antiarrhythmics or drugs known to prolong the QT interval. Concomitant treatment with strong CYP3A4 inhibitors, which may increase cabozantinib plasma concentrations, should be avoided.

If at any time on study there is an increase in QTcF to an absolute value > 500 ms or an increase of > 60 ms above baseline, two additional ECGs must be performed with intervals not less than 3 min apart within 30 min after the initial ECG.

If the average QTcF from the three ECGs is > 500 ms or increased by > 60 ms above baseline, the following actions must be taken:

- Withhold study treatment
- Immediately notify the PI
- Hospitalize symptomatic subjects (e.g., with palpitations, dizziness, syncope, orthostatic hypotension, a significant ventricular arrhythmia on ECG) for a thorough cardiology evaluation and management
- Consider cardiology consultation for asymptomatic subjects for evaluation and management
- Check electrolytes, especially magnesium, potassium and calcium; correct abnormalities as clinically indicated
- Check concomitant medications for any medication that may have contributed to QT prolongation, and if possible, discontinue these medications (<http://www.qtdrugs.org>)

Subjects with QTc prolongation and symptoms must be monitored closely until the QTc elevation and symptoms have resolved. Study treatment may be restarted at a reduced dose level if all of the following conditions are met:

- Symptoms are determined to be unrelated to the QT interval prolongation
- The QTcF value > 500 ms or increase of > 60 ms above baseline is not confirmed according to protocol procedures
- Study treatment has been interrupted through a minimum of 1 week following the return of the QTcF to ≤ 500 msec or return to ≤ 60 ms above baseline.

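### After a related Grade 4 event at the lowest dose, Table 4-3 leaves only discontinuation, while section 4.3.2 allows a same-dose restart on the investigator's judgement alone

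*Combined protocol and SAP*

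**What the plan says.** Section 4.3.1 limits dose reduction: "One dose reduction level of cabozantinib and one dose reduction level of erlotinib are permitted". Table 4-2 gives the levels: 40 mg to 20 mg for cabozantinib and 100 mg to 50 mg for erlotinib. For each drug it adds that the drug is stopped if the reduced dose cannot be tolerated.

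For Grade 4 events, Table 4-3 calls for immediate interruption and then: "Discontinue treatment unless the following criteria are met". Two criteria follow. The first is that the investigator sees a clear benefit to the patient and that the sponsor-investigator concurs. The second reads: "Toxicity can be managed with a dose reduction following recovery to Grade 1 (or baseline) and optimal medical care".

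The row excludes laboratory abnormalities without clinical relevance. Footnote a confines dose adjustment to toxicity that is related to treatment or whose relation is unclear. A note under the table directs the reader to section 4.3.2 for re-treatment after a hold.

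Section 4.3.2 says that a subject on the lowest trial dose "may be restarted at the same dose if deemed safe at the discretion of the investigator". The next sentence has subjects who cannot tolerate that dose discontinue. The only mention of Grade 4 in section 4.3.2 is a bar on re-escalation after certain Grade 4 events.

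**The concern.** The two rules reach the same patient and give different answers. Under the Grade 4 row of Table 4-3, a patient with no reduction left comes off the drug. Under section 4.3.2, the same patient may be given the same dose again. The rules also differ on who decides: Table 4-3 needs the sponsor-investigator's agreement to continue, and section 4.3.2 needs only the investigator.

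With a single reduction level, any patient who has been reduced once is already at the floor for that drug. At stake are the safety of a patient who has just had a Grade 4 event and the consistency with which such patients are handled.

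**Working it through.** No arithmetic beyond counting dose levels applies, and the plan states no figure to reproduce. The check sets the texts side by side.

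1. **Reductions left at the floor.** Each drug has two levels (40 and 20 mg; 100 and 50 mg), so one reduction. Once it is used, 1 − 1 = 0 reductions remain for that drug.
2. **Table 4-3 applied at the floor.** Its two criteria are listed together as the condition for not discontinuing, and I read them as both required. The second needs a dose reduction. With none left it cannot be met, whatever the benefit and whoever agrees, so the row leaves discontinuation of that drug.
3. **Section 4.3.2 applied at the floor.** The same-dose sentence is addressed to exactly this dose level. It carries no grade limit, no benefit test and no second approver.
4. **Whether both texts apply.** The Grade 4 row starts with an interruption, and the note under Table 4-3 sends the reader to section 4.3.2 for restarting after one. The cross-reference therefore leads from one rule to the other.
5. **Whether another sentence decides it.** The Grade 4 restriction in section 4.3.2 covers re-escalation only. The not-tolerated sentences in section 4.3.2 and Table 4-2 would decide it if a Grade 4 event were defined as not tolerating the dose. No passage gives that definition or ties tolerance to a grade.

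| | Table 4-3, Grade 4 row | Section 4.3.2, lowest dose |
|---|---|---|
| Outcome at the floor | Discontinue the drug | Same-dose restart permitted |
| Benefit test | Yes | None stated |
| Who decides | Investigator with sponsor-investigator | Investigator |
| Grade limit | Grade 4 | None stated |

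6. **Who is outside the conflict.**
   - Unrelated events. Section 4.3.2 separately allows these to restart with no dose change.
   - Laboratory abnormalities without clinical relevance.
   - Events with their own stopping rule in section 4.4 or its subsections, such as perforation or fistula, severe hemorrhage, serious arterial thromboembolism, nephrotic syndrome, hypertensive emergency and interstitial lung disease.
   - Patients with a reduction still available in the drug held responsible. If only one drug is at its floor, the other may still be reducible, and section 4.3.1 allows continuation on one drug.

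**The case against.** The best defence reads the texts in sequence. Table 4-3 decides whether treatment stops, and section 4.3.2 governs only patients on hold, so a patient who fails the Grade 4 criteria never reaches it. On this view the Grade 4 row is also the more specific rule, and the same-dose sentence is merely permissive. In addition, both section 4.3.2 and Table 4-2 say to stop when the lowest dose is not tolerated, which harmonises the rules if every Grade 4 event counts as not tolerated. Table 4-3 heads its actions as recommendations. Finally, section 3.5 names one centre, and section 9 requires weekly meetings that include the principal investigator and review toxicities and dose adjustments.

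Some of this stands. A harmonised reading is possible, and single-centre conduct with weekly review lowers the chance of divergent handling. It does not settle the matter. The Grade 4 row itself opens with a hold. One rule is specific by grade and the other by dose level, so specificity does not rank them. The reading of Grade 4 as not tolerated has to be supplied by the reader. The Grade 4 row is worded as a directive and names a second approver, whatever the column heading says.

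A reader might go further and infer the same contradiction for QTc prolongation and Grade 3 hand-foot syndrome (PPES), where the restart text speaks only of a reduced dose. For QTc, section 4.4.1.10 says "Study treatment may be restarted at a reduced dose level if all of the following conditions are met". One of those conditions is the principal investigator's review and agreement, and confirmed recurrence after a reduced-dose restart ends all study treatment. The case of recurrence after such a restart is thus decided. For PPES, Table 4-5 says "Resume study drug at a reduced dose if PPES recovers to Grade" 1 or lower. It is silent on a patient already at the floor, and Table 4-3 does not require discontinuation at Grade 3, so this is a gap and not a contradiction.

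**Conclusion.** The point holds for a defined patient: a Grade 4 event that is related or of unclear relation, is not a clinically irrelevant laboratory finding and has no stopping rule of its own, in a patient whose responsible drug, or both drugs, is already at the lowest level. For that patient the protocol gives two answers and two approvers. This rests on reading the two Table 4-3 criteria as jointly required, and on the absence of any definition of not tolerating the lowest dose.

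The frequency cannot be estimated. A reader might turn to the 29% Grade 3 diarrhea in section 2.1, but that comes from a lung cancer study, is not Grade 4, and says nothing about events after a reduction. The 6% Grade 3 rash from the same study, and the 5% Grade 3-4 rash with erlotinib plus gemcitabine in section 4.4.1.5, do not help either.

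A reader might also infer that one patient kept on or taken off could tip the decision, since 2 responses in 37 reject the combination and 3 do not. Scheduled scans do sit in the treatment period, so this is not impossible. It would need a patient who has a Grade 4 event at the floor before any confirmed response and would then have responded on the same dose. Section 8.3 counts response until progression, not until treatment stops, and nothing in the documents makes this chain likely. The sample size, the 11- and 37-patient stages and the stated error rates do not depend on the point. It is a matter of patient safety and consistent conduct.

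**What to change.** Reconcile the Grade 4 row of Table 4-3 with the same-dose restart sentence in section 4.3.2, so that a patient already at the lowest level gets one answer from both places and the same approver is named in each. State in the same edit whether a Grade 4 event counts as not tolerating the lowest dose, since the stopping sentences in section 4.3.2 and Table 4-2 depend on it. Which rule applies is the sponsor's clinical decision, and this review takes no position on it.

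The cost is a wording change in one amendment. It adds no patients, procedures or analyses.

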4.3.2 Dose Reinstitution and Reescalation

If the subject recovers from his or her toxicities to CTCAE v.4.03 Grade ≤ 1 or to the baseline value (or lower) and the toxicity was unrelated to study treatment, then study treatment may be restarted with no change in dose.

CONFIDENTIAL

If the subject recovers from his or her toxicities to Grade \leq 1 or to the baseline value (or lower) the toxicity was deemed possibly related to study treatment, then study treatment may be restarted at a reduced dose (see Table 4-2 for the schedule of dose reductions).

Subjects receiving the lowest trial dose (cabozantinib = 20 mg/day; erlotinib = 50 mg/day) may be restarted at the same dose if deemed safe at the discretion of the investigator. Subjects unable to tolerate the lowest trial dose should discontinue study treatment.

Re-escalation to the previous dose, (but not higher than the trial dose [cabozantinib = 40 mg/day; erlotinib = 100 mg/day]) may be allowed at the discretion of the investigator and agreement of the PI for AEs which have resolved or recovered to Grade 1 (or baseline value) and deemed tolerable and easily managed by optimized supportive treatment. Dose re-escalation is not allowed for a drug-related dose reduction triggered by Grade 4 hematologic toxicities or by Grade 4 AEs affecting major organs (e.g., central nervous system, cardiac, hepatic, renal).

4.4 Warnings and Precautions and Guidelines for the Management of Adverse Events

The most frequent adverse events experienced by \geq 20% of subjects were:

- Cabozantinib: diarrhea, fatigue, nausea, decreased appetite, vomiting, weight decreased, palmar-plantar erythrodysesthesia syndrome (PPES), constipation, hypertension, dysgeusia, dysphonia, and asthenia.
- Erlotinib: rash, diarrhea, anorexia, fatigue, dyspnea, cough, nausea, and vomiting.

Adverse events associated with laboratory abnormalities experienced by \geq 5% of subjects include:

- Cabozantinib: anemia, AST increased, ALT increased, hypothyroidism, hypokalemia, hypomagnesemia, thrombocytopenia, hypocalcemia, hypophosphatemia, lipase increased, lactate dehydrogenase (LDH) increased, neutropenia, ALP increased, hyponatremia, and leukopenia. Mild to moderate QTc interval prolongation (10-15ms) has also been observed with a QT interval calculated by the Fridericia formula (QTcF) not exceeding 500 ms.

Subjects may also experience medically important but less frequent adverse events including:

- Cabozantinib: arterial and venous thrombotic AEs (e.g., deep vein thrombosis [DVT], pulmonary embolism [PE], transient ischemic attack [TIA], and myocardial infarction

CONFIDENTIAL

[MI]), severe hemorrhagic events, proteinuria, wound healing complications, gastrointestinal [GI] perforation, abscesses including intra-abdominal and pelvic abscess, GI and non-GI fistulae formation, osteonecrosis, and reverse posterior leukoencephalopathy syndrome (RPLS).

- Erlotinib: interstitial lung disease (ILD), renal failure, hepatotoxicity with or without hepatic impairment, GI perforation, bullous and exfoliative skin disorders, MI/ischemia, cerebrovascular accident (CVA), microangiopathic hemolytic anemia with thrombocytopenia, ocular disorders, hemorrhage in patients taking warfarin, and embryo-fetal toxicity. Please refer to the package insert for more detailed information on managing these conditions.

Treatment should be permanently discontinued for the following adverse events:

- Cabozantinib: visceral perforation or fistula formation, severe hemorrhage, serious arterial thromboembolic events, nephrotic syndrome, malignant hypertension, hypertensive emergency, persistent uncontrolled hypertension despite optimal medical management, osteonecrosis of the jaw (ONJ), and serious and life-threatening RPLS.
- Erlotinib: ILD, severe hepatic toxicity (see Section 4.4.1.2), gastrointestinal perforation, severe bullous, blistering, or exfoliating skin conditions, and corneal perforation or severe ulceration.

The predicted effective plasma half-life of cabozantinib is 55 hours. Thus, when initiating therapy with cabozantinib, it will take most subjects 2 to 3 weeks to reach steady state. If AEs attributable to cabozantinib occur within the initial 3-week period of dosing, early intervention with dose modifications may be justified for AEs that, if worsened, could potentially be dangerous or debilitating, because without a dose adjustment, systemic exposure of cabozantinib might be expected to increase after the onset of the AE. Cabozantinib-related events that generally have an early onset include hypocalcemia, hypokalemia, thrombocytopenia, hypertension, PPES, abdominal pain, mucosal inflammation, constipation, diarrhea and vomiting.

A population pharmacokinetic analysis in 591 patients receiving the single-agent erlotinib 2nd/3rd line regimen showed a median half-life of 36.2 hours. Time to reach steady state plasma concentration would therefore be 7 to 8 days. No significant relationship of clearance to covariate of patient age, body weight, or gender were observed. Smokers had a 24% higher rate of erlotinib clearance. Similar results were observed in a population pharmacokinetic analysis

CONFIDENTIAL

conducted with 204 pancreatic cancer patients who receive erlotinib plus gemcitabine. Co-administration of gemcitabine had no effect on erlotinib plasma clearance. Rash and diarrhea, the most common adverse reactions with erlotinib, usually occur within one month of starting treatment.

CONFIDENTIAL

4.4.1 Guidelines for Management of Potential Adverse Events

Please refer to the subsections below for specific guidelines regarding the following potential adverse events:

| | |
|--|--|
| Gastrointestinal disorders (diarrhea, nausea, decreased appetite, vomiting, constipation, stomatitis and abdominal pain) | Section 4.4.1.1 Table 4-4: Management of Treatment-Emergent Diarrhea |
| Hepatobiliary disorders (elevations of ALT, AST, bilirubin; hepatic failure, hepatorenal syndrome) | Section 4.4.1.2 |
| Hematological disorders (neutropenia, thrombocytopenia) | Section 4.4.1.3 |
| Fatigue, anorexia, and weight loss | Section 4.4.1.4 |
| Skin disorders (rash [blisters, erythematous rash, macular rash, skin exfoliation, dermatitis acneiform, and papular rash], palmar-plantar erythrodysesthesia syndrome [PPES], pruritus, dry skin, erythema, pigmentary changes, alopecia) | Section 4.4.1.5 Table 4-5: Management of PPES |
| Wound healing and surgery | Section 4.4.1.6 |
| Hypertension | Section 4.4.1.7 Table 4-6: Management of Hypertension Related to Cabozantinib |
| Thromboembolic events (deep vein thrombosis [DVT], pulmonary embolism [PE], transient ischemic attack [TIA], myocardial infarction, ischemia, cerebrovascular accident) | Section 4.4.1.8 |
| Proteinuria | Section 4.4.1.9 Table 4-7: Manage of Proteinuria |
| Corrected QTc prolongation | Section 4.4.1.10 |
| Hypophosphatemia | Section 4.4.1.11 |
| Thyroid function disorders (changes in thyroid function tests, hypothyroidism) | Section 4.4.1.12 |
| Hemorrhagic events | Section 4.4.1.13 |
| GI perforation/fistula and non-GI fistula | Section 4.4.1.14 |
| Osteonecrosis of the jaw | Section 4.4.1.15 |
| Respiratory, thoracic and mediastinal disorders (cough, dyspnea, fistula formation, pneumonia, interstitial lung disease [ILD]) | Section 4.4.1.16 |
| Renal failure (hepatorenal syndrome, severe acute renal failure, renal insufficiency) | Section 4.4.1.17 |
| Ocular disorders (decrease tear production, abnormal eyelash growth, keratoconjunctivitis sicca, keratitis) | Section 4.4.1.18 |

CONFIDENTIAL

